6.2.6. Endpoints for Immunogenicity Data of Avelumab

All analyses described below are performed for Arm A.

Blood samples (3.5 mL SST tube per timepoint) for evaluation of avelumab immunogenicity will be collected from Arm A patients within 2 hours before the start of the avelumab infusion on Day 1 and Day 15 of Cycles 1 through 3 and then on Day 1 of Cycle 5, 7, 9, 11 and 13. Immunogenicity blood samples will be assayed for anti avelumab antibodies using a validated analytical method. All of the samples that are positive for ADA may also undergo characterization for nAb.

Patients will be characterized into different ADA categories based on the criteria defined in [Table 14](#).

Table 14. Patients Characterized Based on Anti-Drug Antibody Results (ADA Status)

Category	Definition	Patients at Risk (Denominator for Incidence)
ADA never-positive	No positive ADA results at any time point; ADA-negative patients (titer < cutpoint)	Number of patients with at least one valid ADA result at any time point
ADA ever-positive	At least one positive ADA result at any time point; ADA-positive patients (titer ≥ cutpoint)	Number of patients with at least one valid ADA result at any time point
Baseline ADA positive	A positive ADA result at baseline	Number of patients with valid baseline ADA result
Treatment-boosted ADA	A positive ADA result at baseline and the titer ≥ 8×baseline titer at least once after treatment with avelumab	Number of patients with valid baseline ADA results and at least one valid post-baseline ADA result
Treatment-induced ADA	Patient is ADA-negative at baseline and has at least one positive post-baseline ADA result; or if patient does not have a baseline sample, the patient has at least one positive past-baseline ADA result	Number of patients with at least one valid post-baseline ADA result and without positive baseline ADA result (including missing, NR)
Transient ADA response	If patients with treatment-induced ADA have (a single positive ADA result or duration between first and last positive result < 16 weeks) and ADA result at the last assessment is not positive.	Number of patients with at least one valid post-baseline ADA result and without positive baseline ADA result (including missing, NR)
Persistent ADA response	If patients with treatment-induced ADA have duration between first and last positive ADA result ≥ 16 weeks or a positive ADA result at the last assessment	Number of patients with at least one valid post-baseline ADA result and without positive baseline ADA result (including missing, NR)

ADA: anti-drug antibody, NR = not reportable.

Patients will be characterized into different nAb categories based on the criteria in [Table 15](#). For nAb, treatment-boosted is not applicable since no titer result is available.

Table 15. Patients Characterized Based on Neutralizing Antibody Results (nAb Status)

Category	Definition	Patients at Risk (Denominator for Incidence)
nAb never-positive	No positive nAb results at any time point	Number of patients with at least one valid ADA result at any time point
nAb ever-positive	At least one positive nAb result at any time point	Number of patients with at least one valid ADA result at any time point
Baseline nAb positive	A positive nAb result at baseline	Number of patients with valid baseline ADA result
Treatment-induced nAb	Patient is not nAb positive at baseline and has at least one positive post-baseline nAb result; or if patient does not have a baseline sample, the patient has at least one positive post-baseline ADA result	Number of patients with at least one valid post-baseline ADA result and without positive baseline nAb result (including missing, NR)
Transient nAb response	If patients with treatment-induced nAb have (a single positive nAb result or duration between first and last positive result <16 weeks) and nAb result at the last assessment is not positive.	Number of patients with at least one ADA valid post-baseline result and without positive baseline nAb result (including missing, NR)
Persistent nAb response	If patients with treatment-induced nAb have duration between first and last positive nAb result ≥16 weeks or a positive nAb result at the last assessment	Number of patients with at least one valid post-baseline ADA result and without positive baseline nAb result (including missing, NR)

ADA = antidrug antibody, nAb = neutralizing antibody, NR = no result.

The number and percentage of patients in each ADA and nAb category will be summarized.

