6.2.6.1. Time to and Duration of ADA and nAb response

The ADA and nAb analyses described below will include patients with treatment-induced ADA or nAb, respectively.

Time (weeks) to ADA response is defined as:

$$(\text{Date of first positive ADA result} - \text{date of first dose of avelumab} + 1)/7.$$

Time to ADA response will be summarized using simple descriptive statistics (mean, SD, median, min, max, Q1, Q3).

Duration (weeks) of ADA response is defined as:

$$(\text{Date of last positive ADA result} - \text{date of first positive ADA result} + 1)/7.$$

Duration of ADA response will be censored if:

- the last ADA assessment is positive AND patient is ongoing treatment with avelumab, or

- the last ADA assessment is positive AND patient discontinued treatment with avelumab AND the last planned ADA assessment (30 days after the last dose of avelumab) is after the cut-off date.

Time to nAb response and duration of nAb response are defined similarly based on first and last positive nAb result.

Kaplan-Meier estimates (product-limit estimates) will be presented together with a summary of associated statistics including the median ADA response time with 2-sided 95% CIs. ADA response rates at different timepoints will be estimated with corresponding 2-sided 95% CIs. The CIs for the median will be calculated according to Brookmeyer and Crowley (1982) and the CIs for the survival function estimates will be derived using the log-log transformation according to Kalbfleisch and Prentice (2002) (conftype=loglog default option in SAS Proc LIFETEST) with back transformation to a CI on the untransformed scale. The estimate of the standard error will be computed using Greenwood's formula.

Duration of ADA response will be displayed graphically and analyzed using Kaplan-Meier methodology. If the number of patients with ADA response is small, the Kaplan-Meier method may not provide reliable estimates. In this case, only descriptive statistics or listings will be provided

As data permit, the analyses described above will be repeated for patients with treatment-induced nAb.

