6.2.6.3. Analysis of PK and safety by immunogenicity status

The following ADA and nAb status will be used for the analyses described below.

ADA

- ADA ever-positive versus ADA never-positive
- ADA: treatment-induced ADA versus ADA never-positive or baseline ADA positive

nAb

- nAb ever-positive versus nAb never-positive
- nAb: treatment-induced nAb versus nAb never-positive or baseline nAb positive

Data listings will include immunogenicity data together with relevant PK, safety and efficacy data.

PK parameters and immunogenicity status

The following analyses will include patients in both the immunogenicity analysis set and in the PK parameter analysis set. The PK endpoints pertinent to the immunogenicity analyses are C_{trough} and C_{max} .

Blood samples for avelumab PK will be collected pre-dose and at the end of infusion (immediately before the end of avelumab infusion) on Day 1 and Day 15 of Cycles 1 – 3, and then pre-dose and at the end of avelumab infusion) on Day 1 of Cycle 5, 7, 9, 11 and 13.

C_{trough} and C_{max} will be summarized descriptively (n, mean, SD, CV, median, minimum, maximum, geometric mean, its associated CV, and 95% CI) by nominal time and ADA status. Linear-linear plots of mean and median for C_{trough} and C_{max} over nominal time and by ADA status will be presented.

Among patients with treatment-induced ADA, analyses will be conducted to assess whether C_{trough} and C_{max} have any changes before and after the first positive ADA assessment. To be included in this analysis, patients must have the same PK parameter available both before and after the first positive ADA assessment. Relative PK day will be calculated as:

$$(\text{PK assessment nominal day}) - (\text{first positive ADA assessment nominal day}).$$

Nominal day is the protocol scheduled timing for an assessment. For example, if C_{trough} is collected on Day 1 of Cycle 2 and the first positive ADA result is observed on Day 1 of Cycle 3, then the relative PK day for this C_{trough} is -28. Linear-linear plots of mean and median for C_{trough} and C_{max} over relative PK day will be presented.

As data permit, the analyses described above will be repeated for nAb.

Safety and immunogenicity status

The following analyses will include patients in the immunogenicity analysis set.

The frequency (number and percentage) of patients with each of the following will be presented by ADA status.

- TEAEs, by SOC and PT

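### Table 15 lets a positive ADA result alone define treatment-induced nAb when the baseline sample is missing, so a patient can be both treatment-induced and never-positive for nAb

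*SAP*

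**What the plan says.** Incidence of ADA and nAb against avelumab is a secondary endpoint (SAP 3.2.5). SAP 6.2.6 sorts Arm A patients into ADA categories (Table 14) and nAb categories (Table 15) and reports the number and percentage in each. On nAb testing it says "All of the samples that are positive for ADA may also undergo characterization for nAb", so an ADA-positive sample may be nAb-negative or may have no nAb result.

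Table 15 defines treatment-induced nAb by two branches joined by an or:

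- Branch 1: "Patient is not nAb positive at baseline and has at least one positive post-baseline nAb result".
- Branch 2: "or if patient does not have a baseline sample, the patient has at least one positive post-baseline ADA result".

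The other rows that matter here all rest on nAb results:

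- Never-positive: "No positive nAb results at any time point".
- Transient: among treatment-induced patients, "a single positive nAb result or duration between first and last positive result <16 weeks", with the last assessment not positive.
- Persistent: among treatment-induced patients, "duration between first and last positive nAb result ≥16 weeks or a positive nAb result at the last assessment".

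Two later sections use these categories. SAP 6.2.6.1 analyses patients with treatment-induced nAb and states "Time to nAb response and duration of nAb response are defined similarly based on first and last positive nAb result". SAP 6.2.6.3 gives as its second nAb grouping "nAb: treatment-induced nAb versus nAb never-positive or baseline nAb positive".

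**The concern.** Branch 2 assigns nAb status from a different analyte. It treats a positive ADA result as enough when the baseline sample is missing, although the row reports nAb. Never-positive makes no exception for ADA status or a missing baseline, so the two categories are not mutually exclusive.

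Followed literally, the rule has three effects:

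- The treatment-induced nAb count and percentage can be overstated and fail to reconcile with the transient and persistent rows beneath them.
- A patient can be in both groups of the second nAb comparison in 6.2.6.3, which is used for PK and safety summaries.
- A patient can enter the nAb set of 6.2.6.1 with no positive nAb date from which to compute a time or duration.

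**Working it through.** The plan states no figure to reproduce. The check is of the logic of the definitions, followed by the size of the effect per patient.

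**1. Can the patient exist under the plan?** Take an Arm A patient with no baseline sample, at least one ADA-positive post-baseline sample, and no positive nAb result (tested negative, or not tested).

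- The immunogenicity analysis set (SAP 4.3.4) needs one ADA or nAb sample, not a baseline sample.
- The never-positive denominator needs one valid ADA result at any time, so the patient is in.
- The treatment-induced denominator needs a valid post-baseline ADA result and no positive baseline nAb result, and it expressly admits a missing baseline, so the patient is in.

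**2. Which categories does the patient meet?**

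| Table 15 row | Requirement | Met? |
|---|---|---|
| Never-positive | no positive nAb result | yes |
| Treatment-induced, branch 1 | a positive post-baseline nAb result | no |
| Treatment-induced, branch 2 | no baseline sample and a positive post-baseline ADA result | yes |
| Transient or persistent | positive nAb result(s) | no |

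**3. Is the overlap confined to this patient type?** Take four baseline states (no sample; ADA-negative; ADA-positive and nAb-negative; positive for both). Take two post-baseline samples, each in one of four states (ADA-negative; ADA-positive and nAb-negative; ADA-positive and nAb not tested; positive for both). That gives 4 × 4² = 64 result patterns.

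As written, 8 of the 64 are both never-positive and treatment-induced. All 8 have no baseline sample. With no baseline and no positive nAb result, each post-baseline sample has three possible states, giving 3² = 9 patterns. Removing the one in which both samples are ADA-negative leaves 8. With nAb in place of ADA in branch 2, the overlap is 0 of 64. These are counts of logical patterns, not expected proportions of patients.

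**4. Do the rows reconcile?** For a treatment-induced patient with at least one positive post-baseline nAb result:

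- last assessment positive: persistent;
- last assessment not positive, first to last positive at least 16 weeks: persistent;
- last assessment not positive, a single positive or under 16 weeks: transient.

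These cases are exhaustive and do not overlap, so for such patients treatment-induced = transient + persistent. With k patients admitted only through branch 2, treatment-induced = transient + persistent + k.

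**5. Size per patient.** Each affected patient is already in the denominator D, so only the numerator rises and the row increases by 1/D. The documents do not give D. Planned Arm A is about 668/2 = 334.

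| D | 1/D |
|---|---|
| 334 (planned Arm A) | 0.30 percentage points |
| 300 (assumed) | 0.33 percentage points |
| 250 (assumed) | 0.40 percentage points |

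**The case against.** The best answer is that this is a copying slip with an obvious intended meaning. Table 14 carries the same branch with ADA, where it is correct. Everything around it in Table 15 points to nAb, so a programmer would probably read it that way. That origin is plausible but inferred. Nothing in the SAP or protocol corrects the wording, and code that follows the text would reproduce the error.

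The reach is also narrow, and this stands:

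- A pre-dose Cycle 1 Day 1 sample is scheduled for every Arm A patient. SAP 3.4.1 treats a planned same-day sample with no recorded time as pre-dose, so the sample has to be truly absent.
- The nAb versions of the time, PK and safety analyses are run only as data permit. They are descriptive, with no test between nAb groups specified.
- In 6.2.6.1 the patient supplies no value, so those summaries would hardly change.
- The row closest to the protocol's percentage of patients with neutralizing antibodies is ever-positive, which is unaffected. So are baseline nAb positive and the ever-positive versus never-positive comparison.
- The plan does not state that treatment-induced must equal transient plus persistent, and a mismatch would be visible in the output.
- The 334 is approximate. The total is approximately 668, and Arm B patients who wrongly receive avelumab are counted in Arm A for safety (SAP 4.2), so 0.30 points is not a strict minimum.

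These points limit the effect; they do not make the definition correct.

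**Conclusion.** The concern holds. As written, Table 15 can place one patient in two categories that should exclude each other. The treatment-induced nAb row can be too high by k patients, or k/D, where k is the number with no baseline sample, a positive post-baseline ADA result and no positive nAb result. The documents do not give k; it is probably small and may be zero. The per-patient figure of about 0.30 points assumes D near the planned Arm A size and is larger if D is smaller. The effect is confined to descriptive Arm A immunogenicity summaries. The primary analysis, type I error, power and between-arm comparisons are not touched. It should be corrected because it is a definite error in a reported category and is simple to remove.

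**What to change.** In the no-baseline branch of the treatment-induced nAb row of Table 15, replace ADA with nAb, so that the branch requires at least one positive post-baseline nAb result. Keep the ADA-based denominators, which fit a scheme in which nAb testing follows ADA positivity. Treatment-induced then equals transient plus persistent, no patient can be both treatment-induced and never-positive, and everyone in the 6.2.6.1 nAb set has a positive nAb date. The cost is one word in the SAP, with no change to data collection.

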6.2.6.1. Time to and Duration of ADA and nAb response

The ADA and nAb analyses described below will include patients with treatment-induced ADA or nAb, respectively.

Time (weeks) to ADA response is defined as:

$$(\text{Date of first positive ADA result} - \text{date of first dose of avelumab} + 1)/7.$$

Time to ADA response will be summarized using simple descriptive statistics (mean, SD, median, min, max, Q1, Q3).

Duration (weeks) of ADA response is defined as:

$$(\text{Date of last positive ADA result} - \text{date of first positive ADA result} + 1)/7.$$

Duration of ADA response will be censored if:

- the last ADA assessment is positive AND patient is ongoing treatment with avelumab, or

- the last ADA assessment is positive AND patient discontinued treatment with avelumab AND the last planned ADA assessment (30 days after the last dose of avelumab) is after the cut-off date.

Time to nAb response and duration of nAb response are defined similarly based on first and last positive nAb result.

Kaplan-Meier estimates (product-limit estimates) will be presented together with a summary of associated statistics including the median ADA response time with 2-sided 95% CIs. ADA response rates at different timepoints will be estimated with corresponding 2-sided 95% CIs. The CIs for the median will be calculated according to Brookmeyer and Crowley (1982) and the CIs for the survival function estimates will be derived using the log-log transformation according to Kalbfleisch and Prentice (2002) (conftype=loglog default option in SAS Proc LIFETEST) with back transformation to a CI on the untransformed scale. The estimate of the standard error will be computed using Greenwood's formula.

Duration of ADA response will be displayed graphically and analyzed using Kaplan-Meier methodology. If the number of patients with ADA response is small, the Kaplan-Meier method may not provide reliable estimates. In this case, only descriptive statistics or listings will be provided

As data permit, the analyses described above will be repeated for patients with treatment-induced nAb.

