| 
21. Anti-Avelumab Antibodies (Anti-Drug Antibodies, ADAs) and Neutralizing Antibodies (Nab): Arm A ONLY. One blood sample (3.5 mL) for anti-avelumab antibodies (and simultaneous pharmacokinetic draws for measurement of avelumab) will be collected at the End of Treatment and 30 day Follow-up visits. All the samples that are positive for ADA may also undergo characterization for Nab.
 |

PROTOCOL AMENDMENT 6: SCHEDULE OF ACTIVITIES FOR STUDY TREATMENT, END OF TREATMENT AND FOLLOW-UP PERIODS

| Visit Identifiers ¹ | Avelumab plus BSC (1 cycle = 4 weeks) | | End of Treatment/ Withdrawal (±3 days) ² | Short-Term Follow-Up ³ | | |
|---|---|---------------------|---|--|--|--|
| | Day 1 (±3 days) | Day 15 (±3 days) | | 30 days (±3 days) After Last Dose of Avelumab | 60 days (±3 days) After Last Dose of Avelumab | 90 days (±3 days) After Last Dose of Avelumab |
| Clinical Assessments | | | | | | |
| Physical Examination ⁴ | Assessment not required per protocol but may be performed as clinically necessary | | | | | |
| ECOG Performance Status ⁴ | Assessment not required per protocol but may be performed as clinically necessary | | | | | |
| Vital Signs ⁴ | Assessment not required per protocol but may be performed as clinically necessary | | | | | |
| Weight ⁵ | X | X | | | | |
| Contraception Check ^{4,6} | X | X | X | X | | |
| Laboratory Studies | | | | | | |
| Hematology ^{4,7} | X | X | X | X | X | X |
| Blood Chemistry ^{4,7} | X | X | X | X | X | X |
| Thyroid Function and ACTH Tests ^{4,8} | X (at odd number cycle only) | | X | X | X | X |
| Serum/Urine Pregnancy Test ^{4,9} | X | X | X | X | | |
| Urinalysis ⁴ | Assessment not required per protocol but may be performed as clinically necessary | | | | | |
| 12-Lead ECG ^{4,10} | Assessment not required per protocol but may be performed as clinically necessary | | | | | |
| Other Assessments | | | | | | |
| Tumor Assessments (including scans) ¹¹ | As per local standard of care and when progression is suspected | | | | | |
| Adverse Events ¹² | X | X | X | X | X | X |
| Concomitant Medications/Treatments ¹³ | Assessment not required per protocol but may be performed as clinically necessary | | | | | |
| Study Treatment | | | | | | |
| Avelumab ¹⁴ | X | X | | | | |

ACTH = adrenocorticotropic hormone; BSC = best supportive care; CR = crossover; ECG = electrocardiogram; ECOG = Eastern Cooperative Oncology Group

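### SAP 6.2.6.1 counts patients who are off avelumab, past the 30-day time point and still ADA-positive as having ended their ADA response, which can only shorten the Kaplan-Meier duration

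*SAP*

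**What the plan says.** SAP 6.2.6.1 covers patients with treatment-induced antibody: "The ADA and nAb analyses described below will include patients with treatment-induced ADA or nAb, respectively". Duration in weeks is the "Date of last positive ADA result" minus the date of the first positive result, plus one day, divided by 7. There are two censoring conditions:

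- The first covers a positive final result in someone whose avelumab has not been stopped.
- The second applies when "the last ADA assessment is positive AND patient discontinued treatment with avelumab AND the last planned ADA assessment", due 30 days from the final dose, comes later than the data cut-off.

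No other censoring condition is given. The method is stated plainly: "Duration of ADA response will be displayed graphically and analyzed using Kaplan-Meier methodology". Duration of nAb response is defined in the same way, and the analyses are repeated for nAb as data permit.

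In SAP 6.2.6, Table 14 classes a treatment-induced response as persistent if the first and last positive results are at least 16 weeks apart, or if there is "a positive ADA result at the last assessment". A transient response requires a last result that is not positive. Table 15 uses the same split for nAb.

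In the Protocol Schedule of Activities for end of treatment and follow-up, footnote 21 says that the last Arm A ADA samples "will be collected at the End of Treatment and 30 day Follow-up visits". No ADA sample is scheduled after that.

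**The concern.** The two censoring conditions leave a gap. A patient who has stopped avelumab, whose 30-day date is on or before the cut-off, and whose last sample is positive falls under neither. In a Kaplan-Meier analysis an uncensored time is an event, so the curve records a response that ended on the day of a positive test. No negative result was seen and none could be, because planned sampling has stopped. The end of the response is unobserved, which is ordinary right censoring.

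The reported median and rates then partly measure how long patients were treated and sampled, not how long the antibody lasted. A reader would also find the same patients described as persistent in the category table and as ended in the curve.

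**Working it through.** The documents give no figure for duration of ADA response, so there is nothing to reproduce. The check has three parts.

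**1. The cases side by side (treatment-induced ADA)**

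| Last ADA result | Status at cut-off | Kaplan-Meier, SAP 6.2.6.1 | Table 14 |
|---|---|---|---|
| Positive | On avelumab | Censored | Persistent |
| Positive | Off, last dose + 30 days after cut-off | Censored | Persistent |
| Positive | Off, last dose + 30 days on or before cut-off | Event | Persistent |
| Not positive | Any | Event | Transient, or persistent if the span is at least 16 weeks |

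The third row is the gap. The second condition turns on the planned date and not on a sample having been taken. A patient who died or withdrew while positive is therefore also an event once last dose + 30 days has passed.

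Worked patients, both off drug with the 30-day visit before the cut-off:

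- Only positive result at the 30-day visit: (0 + 1)/7 = 0.14 weeks, event, persistent.
- Positive from Cycle 3 Day 1 (day 57), last dose on Cycle 3 Day 15 (day 71), still positive at the 30-day visit (day 71 + 30 = 101): (101 − 57 + 1)/7 = 45/7 = 6.43 weeks, event, persistent.

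**2. Direction**

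The Kaplan-Meier estimate is S(t) = ∏(1 − dᵢ/nᵢ). Recoding some events as censored at the same times leaves every risk set nᵢ unchanged and can only lower dᵢ. Each factor rises or stays the same, so the written rule gives a curve that is nowhere above the censored version, and a median that is equal or shorter. No simulation is needed for this.

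**3. Illustrative size**

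*Inputs from the documents:* the ADA visit schedule (Days 1 and 15 of Cycles 1–3, then Day 1 of Cycles 5, 7, 9, 11 and 13, then end of treatment and 30 days after the last dose); 28-month accrual; and a 12-month minimum follow-up, giving a cut-off 12 to 40 months after randomization.

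*Assumptions not in the documents:* uniform accrual, exponential time on avelumab and ADA duration, mean onset 60 days, and the medians below. Each scenario simulates 8,000 patients. All results are in weeks.

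| Median time on drug | True median ADA duration | Positive at last sample | Of all patients with treatment-induced ADA: last-positive and counted as event | Median as written | Median if censored |
|---|---|---|---|---|---|
| 3 months | 8 | 42% | 42% | 4.1 | 8.1 |
| 6 months | 8 | 26% | 26% | 4.1 | 6.1 |
| 12 months | 8 | 16% | 15% | 4.4 | 6.1 |
| 3 months | 26 | 68% | 68% | 8.1 | 30.1 |
| 6 months | 26 | 53% | 50% | 10.4 | 24.1 |
| 12 months | 26 | 43% | 34% | 14.1 | 24.1 |
| 3 months | never resolves | 100% | 99% | 12.4 | not reached |
| 6 months | never resolves | 100% | 90% | 26.4 | not reached |
| 12 months | never resolves | 100% | 73% | 46.4 | not reached |

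In the last three rows no antibody ever disappears, yet the written rule returns a finite median that follows time on drug.

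A simpler setting puts every patient off drug past day 30, with a true median of 24 weeks and a median of 25 weeks on treatment. Separate runs gave about 10 to 12 weeks as written and about 22 weeks if censored.

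**The case against.** The best defence is that the endpoint is an observed span of positivity and not time to a negative result. On that view the span is complete once the last planned sample is due, and both conditions censor exactly when planned sampling is unfinished. The formula does measure first to last positive. But the SAP nowhere says that the quantity is limited to the sampling window, and a Kaplan-Meier median labelled duration of ADA response would not be read that way. The second condition also looks at the planned date only, so it does not ensure that sampling was completed.

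Several limits do stand, and they rule out stronger readings that a reader might infer:

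- **Every last-positive patient is counted as ended.** The SAP correctly censors those still on avelumab and those whose 30-day sample falls after the cut-off.
- **Nearly all still-positive patients are affected.** The documents do not say how many will be off drug. The 12-month minimum follow-up belongs to the primary OS analysis and is not a condition for the interim, and the protocol reports that the primary objective was met at the interim.
- **The persistent and transient counts are wrong.** They are unaffected. A short span with a positive last result is already allowed under persistent, so still-positive patients remain visible in Tables 14 and 15.
- **The result carries inferential weight.** Protocol 9.3.2 describes duration of ADA response only if data permit. SAP 6.2.6.1 falls back to descriptive statistics or listings if there are few responders. The PK and safety analyses in 6.2.6.3 use antibody status and the timing of the first positive result, not this duration.

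SAP 6.2.6.2 ignores censoring, but only in the cross tabulation with titer. It does not change the Kaplan-Meier rule.

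**Conclusion.** The point holds for one group: patients off avelumab, with the 30-day time point on or before the cut-off and a positive last ADA result. For them the SAP treats the end of sampling as the end of the response, and no other section corrects it. The downward direction relative to censoring is certain. The size is not: it depends on the assumed antibody duration, time on drug and share of patients off drug at the cut-off. In the scenarios with a true median of 26 weeks, the written rule gave 8.1 to 14.1 weeks against 24.1 to 30.1 with censoring; with a true median of 8 weeks, 4.1 to 4.4 against 6.1 to 8.1. These are illustrations, not predictions for this trial.

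The consequence is limited to a descriptive secondary analysis of treatment-induced ADA and nAb in Arm A. There is no comparison between arms, and OS, sample size and type I error are not involved. The rule is wrong as written, with low severity.

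**What to change.** Replace the two conditions in SAP 6.2.6.1 with one rule: *Duration of ADA response is censored at the last positive result whenever the last available ADA result is positive; it is an event only if a later valid ADA result is negative.* State that the same rule applies to nAb. The curve and the categories in Tables 14 and 15 would then treat a positive last result consistently.

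The cost is one SAP sentence and a small programming change, with no new data. There will be more censoring, so the median may not be reached; where antibody persists, that is the correct answer. The clock still stops at the last positive sample and not at the first negative one, so some shortening remains (for example 6.1 weeks against a true 8 in two of the scenarios). A footnote should say so.

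If an observed span is really what is wanted, the alternative is to label it as the observed positive span within planned sampling and summarize it descriptively, without Kaplan-Meier.
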